3. INVESTIGATIONAL PLAN

3.1 Overall Study Design and Plan

This will be a 6-month (with follow-up, if necessary, to monitor residual implant), open-label, multicenter study evaluating the safety, tolerability, and efficacy of 2 formulations of dexamethasone intravitreal implant, AR-1105, in a single eye of up-to 45 subjects between 18 and 80 years of age with ME secondary to RVO.

Data collected through Month 6 on the safety and tolerability of each formulation, as well as efficacy signals for each subject randomized, will be used to determine which formulation will be selected for further clinical development. Any subject who presents at Month 6 with

[figure not shown]
visible residual implant will be followed until they require retreatment (following the criteria provided for rescue therapy), or until 1 month after the implant is no longer visible or to Month 9, whichever occurs first.

Rescue therapy in the form of standard of care will be offered to any subject who, in the opinion of the investigator, requires additional therapy for their RVO due to lack of efficacy after Month 3/Week 12. Minimum guideline criteria for consideration of rescue are an increase in CRT of 50 μ m and decrease in BCVA of ≥ 7 letters at any time compared to baseline.

In the case of elevated IOP or cataract, investigators should treat the subject according to standard practice. In the case of a cataract, removal should be performed as soon as possible since BCVA could be impacted by the cataract.

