13.1 Primary Analysis

The percentage of study eyes gaining at least 15 letters in BCVA from baseline will be summarized using discrete summary statistics, including exact 90% and 95% CIs by phase and treatment group.

Treatment group comparisons for study eye will be completed using:

- Fisher's exact statistic:
Example SAS codes: PROC FREQ Data=xx;
Weight count / ZEROS;
Tables aa*treatment / FISHER;
Run;
where aa indicates Yes/No whether at least 15 letters gained.
- Exact 90% and 95% CIs using the Farrington-Manning score statistic:
Example SAS codes: PROC FREQ data=xx;
tables = aa*treatment/ riskdiff(cl=fm);
Weight Count ;
Run;
where aa indicates Yes/No whether at least 15 letters gained.

- Exact logistic regression will be utilized to determine treatment effect on the percentage of study eyes gaining at least 15 letters in BCVA from baseline after adjusting for baseline BCVA. Odds ratio and 95% CI will be presented.

Example SAS codes: PROC LOGISTIC data=xxx descending ;

(e.g., to model probability of at least 15 letters change in BCVA; y-variable="Y");

Class treatment;

Model xx = treatment baseline_BCVA;

Exact treatment baseline_BCVA / estimate = both;

Run;

These analyses will be used to determine differences in formulations and to assess whether there are differences in outcomes.

The efficacy summaries will be performed on the ITT population:

- using LOCF (for continuous variables);
- imputing missing as failure (for categorical variables); and
- using observed data only.

Subjects who receive rescue medication prior to the summarized visit will be imputed as failures for the summarized visits. No additional imputation methodologies will be performed in this early phase study.

The percentage of subjects gaining or losing at least 15 letters at other study visits and the percentage of subjects gaining or losing at least 10 letters at each study visit will be analyzed similarly.

Change from baseline in BCVA letters to each follow-up visit will be summarized using continuous summary statistics, including 90% and 95% CIs by treatment group.

Box plot of change from baseline in BCVA letter score by visit and treatment group for study eye will be presented. Separate box plot of change from baseline in BCVA letter score for study eye will be presented for subjects with improvement of 15 or more letters, 10 or more letters, and 5 or more letters.

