A linear model with change from baseline BCVA letters for study eye only as the response, baseline BCVA letters as a covariate, and treatment group as a main effect will be fit to determine treatment group effect with separate models completed for each follow-up visit. These analyses will be used to determine differences in formulations and may be used to assess whether there are differences in outcomes between subjects' data pre- and post-interim to determine whether the data may be pooled. Subjects who receive rescue medication prior to the summarized visit will have their measure replaced with their last observation prior to receiving rescue medication. The least squares mean, standard error, and CI for each treatment group, and the difference between treatment groups will be presented for

study eye only. Additionally, analyses will be completed using individual two-sample t-tests and 90% and 95% CIs around the difference between treatment groups in mean BCVA and mean change from baseline BCVA for study eye only.

Median time (in months) to achieve a treatment response of ≥ 15 letters improvement from baseline in BCVA for study eye and median time (in months) to rescue therapy will be estimated using Kaplan-Meier methods with 90% and 95% CI, calculated using the method of Brookmeyer and Crowley (1982). The log rank statistic will be used to determine differences in time to achieve response between the two treatment groups to determine differences in formulations. Cox proportional hazards will also be used to analyze time to event, including baseline BCVA as a covariate. Results from unscheduled visits or early termination visits will be included in the time to event analysis.

For the event of achieving a treatment response of ≥ 15 letters improvement from baseline in BCVA for study eye, the starting date will be the date of first dose. Subjects receiving rescue medications prior to or on the same date as the achievement of improvement will be considered censored on the day of rescue medication receipt; subjects with neither rescue medications received nor improvement achieved will be considered censored on the last date known to be rescue medication free and improvement achievement free. For the event of receiving rescue therapy, the starting date for the time to event evaluation will be the date of first dose. Subjects who do not receive rescue therapy will be considered censored on the last date known to be event free.

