Example SAS codes: PROC LIFETEST Data=xxx method=KM;

Strata treatment/test=logrank;

Time AVAL*CENSOR(0);

Run;

where CENSOR indicates censored subjects.

PROC PHREG Data = xxx;

Class Treatment (param=ref ref='CF2');

model AVAL*CENSOR(0) = baseline_BCVA Treatment/ties=exact;

run;

where CENSOR indicates censored subjects.

In all analyses, data from subject visits after receipt of rescue medication will be imputed using last observation prior to receiving rescue medication for continuous endpoints and will be imputed as failures for success/failure variables.

Additionally, a subset of the efficacy analyses will be performed by combining the initial phase subjects with the randomization phase subjects.

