13.2 SD-OCT, FA and FP

CRT measured by Cirrus (Zeiss) or Spectralis (Heidelberg) instrument will be summarized at each visit, using continuous summary statistics including change from baseline. Comparison between treatment groups for CRT will be performed using the same approaches as specified for BCVA in section 13.1.

Two time to event analyses for CRT of study eye as specified below will be evaluated using the same statistical method for the event of achieving a treatment response of ≥ 15 letters improvement from baseline in BCVA in section 12.1. The starting date of the evaluation will be the date of first dose. Results from unscheduled visits or early termination visits will be included in the time to event analysis.

- Time to resolution of macular edema: defined as first time point at which CRT is less than or equal to 315 μm for study eye.
- Time to loss of resolution of macular edema among treatment responders (population for this analysis includes subjects who achieved resolution of macular edema except on the last day of measurement): defined as first time point at which CRT returns to greater than 315 μm from first achieving the resolution of macular edema.

For the event of resolution of macular edema, subjects receiving rescue medication prior to or on the same date as the achievement of resolution of macular edema will be censored on the day of their rescue medication receipt. Subjects with neither rescue medications received, nor resolution of macular edema will be considered censored on the last date known to be rescue medication free and resolution of macular edema free. For the event of loss of resolution of macular edema after resolution achieved, subjects receiving rescue medications prior to the loss of resolution of macular edema will be considered censored on the day of rescue medication receipt and subjects receiving rescue medications on the same date as loss of macular edema will be considered for loss of macular edema. Subjects with neither loss of resolution of macular edema nor rescue medication received will be considered censored on the last date known to be loss of resolution of macular edema free and rescue medication free.

Total area of capillary non perfusion within ETDRS Grid (16DA) and total area of fluorescein leakage within the ETDRS grid assessed by FA using both Optos instruments (i.e ultra-widfield) and non-Optos (i.e widefield) will be summarized using continuous summary statistics.

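### Censoring non-responders at rescue for lack of efficacy can produce a Kaplan-Meier median time to response although fewer than half of the eyes responded

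*SAP*

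**What the plan says.** **Time to response.** SAP 13.1 estimates the median time to a gain of at least 15 letters by Kaplan-Meier, with 90% and 95% Brookmeyer-Crowley intervals. On rescue it says: "Subjects receiving rescue medications prior to or on the same date as the achievement of improvement will be considered censored on the day", meaning the rescue date. Protocol 9.6.2 also censors this endpoint at rescue.

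**Time to edema resolution.** SAP 13.2 applies the same method. The event is the "first time point at which CRT is less than or equal to 315" µm. The rescue rule reads: "subjects receiving rescue medication prior to or on the same date as the achievement of resolution of macular edema will be censored"; the censoring date is again the rescue date.

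**Comparison.** "The log rank statistic will be used to determine differences in time to achieve response between the two treatment groups". A Cox model with baseline BCVA is added.

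**Rescue.** Under Protocol 3.1 a subject qualifies for rescue if he or she, "in the opinion of the investigator, requires additional therapy for their RVO due to lack of efficacy after Month 3/Week 12". It adds: "Minimum guideline criteria for consideration of rescue are an increase in CRT of 50" µm together with a BCVA loss of at least 7 letters from baseline.

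**Responder analyses.** SAP 13.1 takes the opposite line on the same eyes: "Subjects who receive rescue medication prior to the summarized visit will be imputed as failures for the summarized visits". It closes with a rule for all analyses, under which data after rescue "will be imputed as failures for success/failure variables".

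**The concern.** Kaplan-Meier gives a censored eye the future of the eyes still at risk. That is reasonable when censoring is unrelated to outcome. Here an eye is censored because the investigator judged that treatment was not working. Its share of the probability then passes to eyes that are doing better.

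An eye that meets the minimum guideline at rescue is far from either event. It is at least 7 + 15 = 22 letters short of response. The lowest entry limit for CRT in Protocol 4.2 is above 290 µm, so its CRT is above 290 + 50 = 340 µm, against a resolution cut-off of 315 µm. The guideline is not binding, so this need not hold for every rescued eye.

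At stake is the median time to each event, planned for SAP Tables 14.2.1.3 and 14.2.2.3.1. A median says that half of the eyes responded by that month. Under this rule it can appear when fewer than half did, while the responder tables count the same rescued eyes as failures.

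**Working it through.** The plan gives no figure for the time-to-event analyses. Its one computed design figure, the 13.9% bound for an adverse event not seen in 20 subjects, reproduces (1 − 0.05^(1/20) = 13.9%) but has no bearing here.

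**Inputs.** From the documents: 20 evaluable subjects per group (SAP 5), rescue only after Month 3, censoring at rescue. Assumed, because the documents give no response or rescue rates: first responses in 3, 2, 2 and 2 eyes at Months 1, 2, 3 and 5 (9 of 20 = 45%); r non-responders rescued at Month 4; rescued eyes do not respond; no other dropout.

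**Formula.** After Month 3 the proportion without response is 13/20 = 0.65. At Month 5 the number at risk is 13 − r, with 2 events. The response estimate is therefore 1 − 0.65 × (11 − r)/(13 − r).

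| Rescued at Month 4 | Calculation | Kaplan-Meier response | Median |
|---|---|---|---|
| 0 | 1 − 0.65 × 11/13 | 45.0% | not reached |
| 2 | 1 − 0.65 × 9/11 | 46.8% | not reached |
| 4 | 1 − 0.65 × 7/9 | 49.4% | not reached |
| 5 | 1 − 0.65 × 6/8 | 51.3% | Month 5 |
| 6 | 1 − 0.65 × 5/7 | 53.6% | Month 5 |

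Nine of 20 eyes respond in every row. If rescued eyes stay at risk as non-responders, the Month 5 factor is 11/13 whatever r is, so every row gives 45.0% with no median.

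**When there is no effect.** Up to the first rescue the two approaches agree. They also agree afterwards if nobody first responds later: with all 9 responses by Month 3, both give 45.0% for any r.

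**A lower response rate.** With first responses in 1, 2, 2, 1, 1 and 1 eyes at Months 1 to 6 (8 of 20 = 40%) and 8 non-responders rescued just after the Month 3 visit, 15 − 8 = 7 eyes remain at risk. The estimate is 1 − 0.75 × (6/7)(5/6)(4/5) = 57.1%, with a median of Month 6. With 4 rescued it is 1 − 0.75 × 8/11 = 45.5%, with no median.

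**Rescue timing.** In the first example, six rescues of which one is at Month 4 and five follow the Month 5 visit give 1 − 0.65 × 10/12 = 45.8%. Two rescues, both at Month 4, give 46.8%. The number of rescues alone does not fix the size of the excess.

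**What does not move.** Compare two arms with the first example's responses, one with 0 and one with 6 rescues at Month 4. The log-rank p-value is 0.76. The 95% Brookmeyer-Crowley interval (log-log) runs from Month 2 to not reached in both arms. The response estimate and the point median are what change.

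**The case against.** **The affected output is narrow.** This stands. SAP 22 lists no Kaplan-Meier figure. The planned output affected is the median, and the interval beside it will usually be wide: in the example it is the same with and without rescues, and the exact 95% interval for 9/20 is 23% to 68%.

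**Planning rests mainly on the responder proportion.** This stands in part. SAP 2.4 ties learning for future studies to the primary efficacy variable, the proportion gaining at least 15 letters, and rescue counts as failure there. Nothing says that the median will set a future sample size. Those tables still do not correct the median, because they record status at each visit and not first-ever response.

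**Only some rescues count.** This stands. An eye that responds, relapses and is then rescued is already an event. Only eyes rescued before responding are censored. With 9 of 20 responding and two of them late, 5 of the 11 non-responders must be rescued at Month 4 before a median appears, and 45% is close to half to begin with.

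**The target may be response had there been no rescue.** The SAP does not say so. That reading would also need rescue to be unrelated to later response, and rescue for lack of efficacy is not.

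**Stronger readings a reader might infer.** One is that the comparison of CF1 with CF2 is invalid. The plan does not support this: log-rank and Cox with censoring at rescue compare the rate of first response among eyes not yet rescued, which is a valid cause-specific comparison. Another is that the arm with more rescues always looks better. The timing example contradicts that.

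**Conclusion.** The point holds for the Kaplan-Meier medians of time to a gain of at least 15 letters and time to edema resolution. Censoring at rescue is informative and conflicts with the SAP's rule for success/failure variables. The estimate cannot fall below the share responding without rescue, and it exceeds that share whenever a first response follows the rescue of a non-responder.

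The size is unknown. In the assumed arm of 20 with 9 responders and 6 rescues, the excess is 53.6 − 45.0 = 8.6 percentage points, and a median of Month 5 replaces none. These figures illustrate the effect and do not bound it: the 8-responder example reaches 57.1 − 40.0 = 17.1 points, and without late responders the excess is zero. The figures are for the letter-gain endpoint; for edema resolution the same algebra applies, but no separate figure was worked.

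The between-formulation tests and the visit-wise responder tables are not faulted. This is an improvement worth making at little cost, and it does not threaten the study's main conclusions.

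**What to change.** For both endpoints, keep any eye rescued before it responds at risk as a non-responder: censor it at the Month 6 visit instead of on the rescue date, and do not count a response recorded after rescue. Read the estimate no further than Month 6. This matches the SAP's failure rule and leaves the planned Kaplan-Meier median and Brookmeyer-Crowley intervals usable. Keep the present rule as a sensitivity analysis, and label log-rank and Cox under it as cause-specific.

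Cumulative incidence with rescue as a competing event is an acceptable alternative. The two agree without other dropout and differ somewhat with it. In the 6-rescue example with 2 further eyes lost between Months 4 and 5, the present rule gives 1 − 0.65 × 3/5 = 61.0%. Cumulative incidence gives 0.35 + 0.35 × 2/5 = 49.0%, where the second 0.35 is the proportion neither responded nor rescued (0.65 × 7/13). Keeping rescued eyes at risk gives 1 − 0.65 × 9/11 = 46.8%.

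The cost is a change of SAP wording and minor programming. The downside is that some medians become not reached.

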Study Design: This will be a 6-month (with follow-up, if necessary, to monitor residual implant), open-label, multicenter, adaptive study evaluating the safety, tolerability, and efficacy of 2 formulations of dexamethasone intravitreal implant, AR-1105, in a single eye of up-to 45 subjects between 18 and 80 years of age with macular edema (ME) secondary to retinal vein occlusion (RVO). Since this study represents the first-in-human experience with AR-1105, the study will begin with an initial phase, during which time, up to a maximum of 5 subjects will be treated with AR-1105 clinical formulation 1 (AR-1105-CF1) and followed during weekly visits for up to 2 weeks post-treatment to assess tolerability and safety. Providing none of the subjects experience any clinically-meaningful ocular adverse reactions (possibly) related to treatment with AR-1105 during the initial phase, the study will continue into the randomized phase. During the randomized phase of the study, subjects will be assigned in a 1:1 ratio to either AR-1105-CF1 or AR-1105 clinical formulation 2 (AR-1105-CF2). Data collected from the subjects enrolled into the randomized phase of the study will be primarily summarized separately from subjects enrolled during the initial phase. Treatment will consist of a single intravitreal administration with AR-1105-CF1 or -CF2, each of which has a target dose of 340 µg dexamethasone (2 implants, single injection). During the randomized phase, each treatment group will enroll approximately 20 subjects (i.e. in addition to the enrolled subjects who will participate in the initial phase on AR-1105-CF1). An interim analysis of the first 20 subjects randomized to CF1 or CF2 may be conducted when they have completed 6 months post-treatment to assist in planning future studies. When all subjects in each treatment group have completed their Month 6 visit, the primary safety and efficacy analyses will be conducted. Data collected through Month 6 on the safety and tolerability of each formulation, as well as efficacy signals for each subject randomized, will be used to determine which formulation will be selected for further clinical development. Any subject who presents at Month 6 with visible residual implant will be followed until they require retreatment (following the criteria provided for rescue therapy), or until 1 month after the implant is no longer visible or to Month 9, whichever occurs first. Rescue therapy in the form of standard of care, will be offered to any subject who, in the opinion of the investigator, requires additional therapy for their RVO due to lack of efficacy after Month 3/Week 12. Minimum guideline criteria for considering rescue are an increase in CRT of 50 µm and decrease in BCVA of ≥ 7 letters at any time compared to baseline. In the case of elevated intraocular pressure (IOP) or cataract, investigators should treat the subject according to standard practice. In the case of a cataract, removal should be performed as soon as possible since BCVA could be impacted by the cataract.

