At these visits, the subject will be queried regarding any changes to their ocular or medical health status since the previous visit, and also if there have been any changes to their ongoing medications or procedures. Vital signs (heart rate and blood pressure) will be collected. Blood samples will be collected (Month 1 and Month 2 visits only) for laboratory assessment of clinical chemistry and hematology.

The following assessments will be conducted OU:

- BCVA by ETDRS will be conducted following manifest refraction
- Slit-lamp biomicroscopy
- IOP measured using a Goldmann applanation tonometer

Following mydriasis, the following procedures will be performed OU, unless otherwise specified:

- SD-OCT (study eye)
- Fundus examination
- The implant will be viewed to verify its status. (study eye)

7.2.4 Visit 6 ([REDACTED] ± 3 Days) and Visit 9 ([REDACTED] ± 3 Days) Procedures

At these visits, the subject will be queried regarding any changes to their ocular or medical health status since the previous visit, and also if there have been any changes to their ongoing medications or procedures. Vital signs (heart rate and blood pressure) will be collected.

Blood samples will be collected for laboratory assessment of clinical chemistry and hematology and if the subject is a female of child-bearing potential, a urine pregnancy test should be administered (Visit 9 only).

The following procedures will be conducted OU:

- BCVA by ETDRS will be conducted following manifest refraction
- Slit-lamp biomicroscopy examination
- Gonioscopy (study eye)
- IOP measured using a Goldmann applanation tonometer

Following mydriasis, the following procedures will be performed OU unless otherwise noted:

- SD-OCT (study eye)
- Fundus examination (study eye)
- Fluorescein angiography
- 3-field fundus photography (study eye)
- The implant will be viewed to verify its status (study eye)

If residual implant is still visible in the vitreous at the Month 6 visit, the subject will be required to return to the site at Month 7 for safety follow-up. Otherwise, the Month 6 visit will be the final visit, and the subject should be thanked for their participation in the study.

7.3 [REDACTED] or Early Termination Procedures

Procedures that should be conducted in the event that the subject needs to exit the study prior to Month 6 (Visit 9) are provided above in Section [7.2.4](#).

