4.1 Method of Assigning Subjects to Treatment Groups

Providing none of the subjects experience any clinically-meaningful ocular adverse reactions (possibly) related to treatment with AR-1105 during the initial phase, the study will continue into the randomized phase. During the randomized phase of the study, subjects will be assigned in a 1:1 ratio to either AR-1105-CF1 or AR-1105-CF2.

5. Sample Size and Power Considerations

This study is not powered to detect a pre-stated efficacy signal, but rather will be used to inform the design and power for future studies. With a sample size of 20 evaluable subjects per treatment group, the study will have 95% confidence of ruling out adverse events (AE) with true incidence rates of 13.9% or higher within each treatment group. That is, with 20 subjects in a treatment group, if an AE of a specific type is not observed, then with 95% confidence, the true incidence rate of that AE is less than 13.9%.

6. Data Preparation

All reported study data will be recorded on the electronic case report forms (eCRF) supplied by Statistic & Data Corporation (SDC). Only the Principal Investigator and authorized study staff according to the Delegation of Responsibilities log are entitled to make entries in the eCRF.

After data are entered into the clinical study database, electronic edit checks and data review will be performed. All data validation specifications and procedures are detailed in the Data Validation Manual as a separate document. When the database has been declared to be complete and accurate, the database will be locked. Any changes to the database after data have been locked can only be made with the approval of the Sponsor and Trial Runners in consultation with SDC.

The final analyses outlined in this document will be carried out after the following have occurred:

- All data management requirements are met according to SDC standard operating procedures, including data entry, performance of edit and validation checks, documentation and resolution of data queries, and database lock with written authorization provided by appropriate SDC and Sponsor personnel.
- Protocol deviations have been identified and status defined (major/minor deviations).
- Analysis populations have been determined.

7. Analysis Populations

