15.1 Adverse Events

An AE is defined as any untoward medical occurrence associated with the use of a drug in humans, whether or not the event is considered drug-related. An AE can therefore be any unfavorable and unintended sign (e.g., an abnormal laboratory finding), symptom, or disease occurring after informed consent form is signed and dated, without any judgment about causality. Any pre-existing medical condition that worsens after first administration of the study medication will also be considered a new AE. The AE reporting period starts from the time the subject signs and dates the informed consent and until 30 days after the subject's last study visit. All Aes will be coded using the MedDRA 21.1.

Treatment-emergent adverse events are defined as any event that occurs or worsens on or after the study treatment is initiated. Adverse events recorded in the eCRF which began prior to treatment will not be included in the summary tables but will be included in the AE data listings.

An overall summary will be presented that includes the number of TEAEs and the number and percentage of subjects who experienced at least one TEAE, by treatment group. This summary will also include breakdowns of TEAEs further categorized as ocular (study eye, fellow eye, and both eyes separately) or non-ocular, serious TEAEs, TEAEs by maximum severity, TEAEs by maximum relationship to study medication, TEAEs by maximum relationship to study procedure, TEAEs by maximum expectedness, number of serious TEAEs, number of subjects with any serious TEAEs, and with TEAEs leading to death.

Additional summaries of TEAEs will be provided showing the number and percentage of subjects who experienced at least one TEAE. These summaries will be presented by system organ class (SOC) and preferred term (PT). Non-ocular TEAEs will be summarized using discrete summary statistics and presented by treatment group at the subject level by SOC and PT. Ocular TEAEs will be similarly summarized at the subject level for study eyes, fellow eyes, and both eyes separately. If a subject reports the same PT multiple times within the same SOC, that PT will only be reported once within that SOC. As with the PT, if a subject reports multiple conditions within the same SOC, that SOC will only be reported once. In the summary, SOC will be listed in ascending alphabetical order; PTs will be listed in order of descending frequency for all subjects within each SOC.

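### The time-to-event analyses and cumulative TEAE tables have no Month 6 cut, although follow-up after Month 6 depends on whether the implant is still visible

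*SAP*

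**What the plan says.** **Who stays.** Under Protocol 7.2.4, a subject with residual implant visible at Month 6 returns at Month 7. "Otherwise, the Month 6 visit will be the final visit" for everyone else. Those who stay are seen monthly until retreatment, one month past disappearance of the implant, or Month 9, whichever is first (Protocol 3.1, 7.4).

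**Time-to-event analyses.** SAP 13.1 covers time to a 15-letter gain and time to rescue. SAP 13.2 adds time to resolution of macular edema and time to loss of that resolution. All four censor at the last event-free date. For rescue: "Subjects who do not receive rescue therapy will be considered censored on the last date known to be event free". For loss of resolution, subjects with neither event nor rescue "will be considered censored on the last date known to be loss of resolution of macular edema free and rescue medication free". Neither section sets an upper limit at Month 6.

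**TEAEs.** SAP 15.1 gives a start and no end: "Treatment-emergent adverse events are defined as any event that occurs or worsens on or after the study treatment is initiated". AE reporting runs to 30 days after each subject's own last visit. The tables are numbers and percentages of subjects, without exposure adjustment.

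**What does stop at Month 6.** The list in SAP 13 limits the BCVA and CRT visit endpoints to Months 1 to 6, including the lead 15-letter endpoint at Month 6. The protocol (Synopsis and 3.1) rests the choice of formulation on Month 6 data: "Data collected through Month 6 on the safety and tolerability of each formulation", together with efficacy signals.

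**The concern.** Implant persistence is a property of the formulation, and the study exists to choose between two formulations. Two consequences follow.

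- After Month 6, the Kaplan-Meier risk set holds only eyes that had visible implant at that visit. Eyes without it are censored at Month 6. If risk of rescue or of recurrent edema depends on implant presence, that censoring is informative. The later part of the estimate, and its contribution to the log-rank and Cox results, can then be biased.
- Subjects who exit at Month 6 have a shorter AE window than those followed to Month 9. If one formulation leaves more visible implants, its crude TEAE percentages rise through longer observation alone.

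Safety is the primary objective, and Protocol 3.2 names long duration of effect as a mark of the optimal formulation. Both readings bear on the choice the study is meant to inform.

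**Working it through.** **The plan's own figure.** SAP 5 states a 13.9% bound for an event not seen in 20 subjects. 1 − 0.05^(1/20) = 0.1391, so it reproduces as a one-sided exact 95% bound. This point does not affect it.

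**Inputs.** From the documents: 20 evaluable subjects per arm (SAP 5), the exit rules (Protocol 7.2.4, 7.4) and AE reporting to last visit plus 30 days (SAP 15.1). The documents do not give the share of eyes with visible implant at Month 6, hazards with and without implant, or TEAE rates. Those below are assumptions. All scenarios take eyes with visible implant at Month 6 as followed to Month 9; earlier exits would shrink the effects.

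**Step 1: AE windows.** Exit at Month 6: 6 months + 30 days, about 7 months. Exit at Month 9: 9 months + 30 days, up to about 10. Protocol 6.8.1 ends AE documentation at the end of participation, which would give 6 versus 9; the gap is up to 3 months either way.

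**Step 2: maintained resolution of edema at Month 9.** Let S be the proportion still resolved at Month 6, v the share of those with visible implant, and h1 and h2 the monthly loss with and without implant.

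- Kaplan-Meier: S(1 − h1)³, since only implant-bearing eyes remain at risk.
- True: S[v(1 − h1)³ + (1 − v)(1 − h2)³].
- Overstatement: S(1 − v)[(1 − h1)³ − (1 − h2)³], which is zero if h1 = h2.

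| Case | S | v | h1 | h2 | Overstatement |
|---|---|---|---|---|---|
| Low corner | 0.60 | 0.70 | 0.10 | 0.20 | 0.18 × (0.729 − 0.512) = 3.9 points |
| Middle | 0.70 | 0.50 | 0.10 | 0.40 | 0.35 × (0.729 − 0.216) = 18 points (51% against 33%) |
| High corner | 0.80 | 0.30 | 0.05 | 0.40 | 0.56 × (0.857 − 0.216) = 35.9 points |

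A median can move as well. With S = 0.60, v = 0.30, h1 = 0.10 and h2 = 0.40, Kaplan-Meier reads 0.60 × 0.9 = 54% at Month 7 and 0.60 × 0.81 = 49% at Month 8, so the reported median is Month 8. The true value at Month 7 is 0.60 × (0.3 × 0.9 + 0.7 × 0.6) = 41%, already below half.

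**Step 3: time to rescue in two arms.** Assume a monthly hazard rate of 0.05 in all eyes in Months 3 to 6, then 0.05 with implant and 0.20 without.

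- Rescue-free at Month 6: exp(−0.15) = 86.1%.
- Kaplan-Meier at Month 9, either arm: 0.861 × 0.861 = 74.1%.
- True, 80% visible: 0.861 × (0.8 × 0.861 + 0.2 × 0.549) = 68.7%.
- True, 20% visible: 0.861 × (0.2 × 0.861 + 0.8 × 0.549) = 52.6%.

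The overstatement is 5 and 21 points, and a true 16-point difference disappears.

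**Step 4: log-rank test.** Simulation with 20 per arm, 4,000 runs and 80% versus 20% visible. Entries are rejection rates at two-sided 0.05.

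| Hazards | As written | Month 6 cut | All eyes to Month 9 |
|---|---|---|---|
| 0.05 throughout | 4.5% | 5.0% | 4.4% |
| 0.05 to Month 6, then 0.05 with / 0.20 without | 5.2% | 4.8% | 17.0% |
| 0.03 / 0.10 in Months 3–6, then 0.05 / 0.20 | 11.8% | 13.8% | 30.6% |

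Simulation error is about ±0.3 points (one standard error) near 5%: √(0.05 × 0.95/4000) = 0.0034.

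**Step 5: TEAE percentages under one constant hazard in both arms.** If p7 is the 7-month rate, the 10-month rate is p10 = 1 − (1 − p7)^(10/7). The false difference is (v1 − v2)(p10 − p7).

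- p7 = 30% gives p10 = 39.9%. At 80% versus 20% visible, the arms read 37.9% and 32.0%, a gap of 6.0 points or 0.060 × 20 = 1.2 subjects.
- Over p7 from 10% to 70%, the gap is 2.4 to 7.7 points at 80/20, 0.8 to 2.6 at 60/40, and zero when shares are equal.

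**Step 6: with a Month 6 cut.** AE windows are equal, so equal hazards give equal expected percentages. Kaplan-Meier values up to Month 6 do not change, and no estimate is made beyond.

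**The case against.** The other side has several sound points, and they limit the claim.

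- A reader might infer that nothing in the SAP stops at Month 6. That is wrong: the listed BCVA and CRT visit endpoints do. IOP, slit-lamp and vital signs are summarised visit by visit, so Months 7 to 9 appear there as separate visits.
- A reader might infer that the results are certain to be skewed. The documents do not support that. Curve bias needs event risk that depends on implant presence; TEAE bias needs unequal visible shares. Neither is quantified. The one comparison given, in miniature pigs (Protocol 1), reports both formulations visible and partly degraded at Week 10.
- A reader might infer inflated false-positive rates. Under equal hazards the log-rank rejection rate is 4.5%.
- SAP 22 plans no Kaplan-Meier figure, and in the middle case of Step 2 the median is not reached with or without the cut. As Step 2 shows, other inputs do move it. Overstated durability describes rescue and loss of resolution only; a 15-letter gain and edema resolution are favourable events.
- The TEAE effect is one or two subjects at this size, no TEAE test is planned, and procedure-related events would tend to come early, which weakens the constant-hazard assumption.
- The protocol already bases the decision on data through Month 6. That supports the cut but does not supply it. SAP 1 lets its own methods supersede the protocol's, and SAP 16 ties only the timing of the final analysis to Month 6. With enrollment lasting up to 6 months (Protocol 3.3), early subjects can have Month 9 data by then.
- Late events in eyes still carrying implant matter in a first-in-human safety study. This stands, so the all-TEAE tables should stay.

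**Conclusion.** The point holds for the four time-to-event endpoints and the cumulative TEAE tables, and no further. As written, censoring and AE observation time after Month 6 depend on implant persistence.

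The bias is conditional and confined to the period after Month 6. Under the assumed ranges (60–80% resolved at Month 6, 30–70% of them visible, monthly loss 5–10% with implant and 20–40% without), maintained resolution at Month 9 is overstated by about 4 to 36 points. With equal hazards and 80% versus 20% visible, the false TEAE difference is about 2 to 8 points. Both vanish if risk does not depend on implant presence and visible shares are equal.

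The cut removes the biased estimates. It does not recover the Month 9 comparison, which would need all eyes followed to Month 9. The change is worth making because it is cheap and brings the SAP into line with the protocol's own basis for choosing a formulation.

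**What to change.** - **SAP 13.1 and 13.2:** for the between-formulation comparison, administratively censor all four time-to-event endpoints at the Month 6 visit, taking the upper end of its ±3-day window. Events at unscheduled or early termination visits before that date still count.
- **SAP 15.1:** keep the all-TEAE tables. Add TEAE tables limited to onset up to the Month 6 visit in all subjects, and name these as the basis for comparing formulations.
- **Later data:** show TEAEs after the Month 6 visit and Months 7 to 9 results in separate tables labelled as residual-implant eyes only. All data stay listed.

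The cost is SAP wording and a few extra tables, with no change to visits or procedures. The downside is that late events do not enter the formulation comparison, though they remain in the all-TEAE tables and the separate display.
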